Caregiver Chronic Grief will be measured with the 50-item Marwit-Meuser Caregiver Grief Inventory (MM-CGI).⁶ This inventory has three subscales: (1) *Personal Sacrifice Burden*: 18 items measuring individual losses experienced as a result of caregiving, (2) *Heartfelt Sadness and Longing*: 15 items measuring interpersonal emotional reactions in response to caregiving, and (3) *Worry and Felt Isolation*: 17 items measuring feelings of losing connections with, and support from, others. Items are rated on a 5-point scale (1 = *strongly disagree* to 5 = *strongly agree*), with a possible range of 50 to 250 points. Grief scores may be calculated by subscale and then added to formulate a total grief score. Total grief scores above 175 indicate high levels of caregiver grief, requiring formal intervention and support. Cronbach's alpha subscale scores range from .90 to .96, indicating high internal consistency reliability for each subscale and for their combined total grief score. Test-retest Cronbach's alpha scores range from .71 to .75, indicating stability of the measure over time in all three subscales.¹⁵

Secondary Outcomes Measures

Depressive symptoms will be measured with the 20-item version of The Center for Epidemiological Studies Depression Scale (CES-D).⁴⁰ Responses are based on a four-point frequency rating (0 = *rarely or none of the time* to 3 = *all of the time*), with a possible range of 0 to 60. A score above 16 indicates existence of depressive symptoms. Internal consistency reliability range $r = .85$ to $.90$, and test-retest reliability $r = .45$ to $.70$.⁴⁰

Anxiety symptoms will be measured with the 20-item State-Anxiety subscale of the State-Trait Anxiety Inventory (STAI).⁴¹ Responses are based on a scale of 1 to 4 (1 = *almost never* to 4 = *almost always*), with a possible range of 20-80, where higher scores indicate greater anxiety. Alpha coefficients for older adults range .90-.92, indicating high internal consistency reliability.⁴¹

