We will measure four exacerbators of ADRD caregiver chronic grief: (1) caregiver lack of knowledge about dementia, (2) caregiver perception of loss, (3) guilt, and (4) role captivity.

Knowledge of dementia/AD will be measured with the 22-item Family Knowledge of Alzheimer's Test (FKAT).³⁰ This instrument captures what a family caregiver knows about the disease process, how the care recipient is behaving, and how the LTCF is caring for him or her. Responses are based on a true/false scale, with a maximum score of 22 correct answers. Test-retest reliability was .82 ($p < .05$), KR 21 ($n = 50$) = .61.

Loss will be measured with the 7-item Loss subscale of the FPCR^{3,30} (full description above). Cronbach's alpha for this subscale was 0.73.

Guilt will be measured with the 5-item Guilt subscale of the FPCR^{3,30} (full description above). Cronbach's alpha for this subscale was 0.70.

Role captivity will be measured with the 7-item Captivity subscale of the FPCR^{3,30} (full description above). Cronbach's alpha for this subscale was 0.81.

Background Measures

Caregiver and care recipient socio-demographics. To describe caregiver and care recipient baseline background data, we will collect standardized information. These survey questions are drawn from the initial population survey used by the East Boston site for the Established Populations for Epidemiologic Studies of the Elderly project (EPES).⁴³ Situational characteristics. Three direct questions will be asked at baseline to assess: (1) number of years since the care recipient was diagnosed with ADRD, (2) time since placement in the LTCF, and (3) visiting pattern in the LTCF (times per week and number of hours per visit).

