9.2 Sample Size and Randomization

Precision analysis. Because we are estimating an effect size, rather than a p value, we are primarily concerned with precision of estimation rather than power. The standard deviation associated with total grief as measured with the MM-CGI is around 35.78 raw units. Thus, a change of one SD represents a two-thirds of a unit change in the MM-CGI Likert Scale. If we obtain a sample of 64 participants per condition, our standard error of measurement (SEM) around this effect size estimate will be about 4.47 units, producing confidence intervals between -8.77 and +8.77 units. This will allow us to estimate a Cohen's d within .25 SD units of the actual value, a reasonably robust estimate, 95% of the time. Adjusting for a 10% attrition rate, we will collect a total sample of 72 participants per condition (a total of 144 participants).⁵⁷

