9.2.1 Treatment Assignment Procedures

The study is a Stage I longitudinal randomized clinical trial. ADRD caregivers whose family members are in LCTFs will be recruited, screened for inclusion criteria, and randomly assigned to either CGMI-V or a Minimal Treatment (MT) control condition. Randomization will be stratified in six Waves of 24 participants each, to insure that there are exactly 12 participants in each condition. In Wave 1, we will randomly assign the first 24 enrolled participants to either the CGMI-V condition ($n = 12$; 6/group) or MT control condition ($n = 12$). The same process will continue for the next five Waves. Recruiters and data collectors will be blinded as to the random assignment of each participant. Once caregivers sign the consent to enroll in the study, the Project Director will use randomization software to assign each enrolled participant to CGMI-V or the MT condition. The Project Director will then inform the participants directly of their assignments and ask them to maintain confidentiality about their assignment at data collection points.

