9.5 Data Analyses

We will track all study participants following CONSORT guidelines and enter all data into a REDCap database. SPSS for Windows (Version 22) and R (Version 3.1.1) will be used for data management and statistical analysis. A two-tailed 0.05 significance level will be used for all statistical tests except where noted below. All analyses will be performed on an intent-to-treat basis. Missing data will be imputed using the R mi package, a multiple imputation computer program based on the work of Rubin.

Histograms will be obtained for these variables, and skew and kurtosis will be assessed to assess statistical normality. From previous research, we expect the error rates to have statistically normal distributions or distributions that can be transformed to normality using logarithmic and square root transformations. We will perform any necessary transformations using Tukey's ladder of transformation before conducting statistical analysis. Because these trials are designed to estimate precise effect sizes rather than probability values, the results of each trial will be the effect size (comparing treatment and control groups) and confidence intervals around this estimate.

Aim 1. Controlling for background variables, establish effect sizes of the CGMI-V condition and Minimal Treatment (MT) control condition on changes in a primary caregiver chronic grief outcome.

Multilevel linear models will be run for the CGMI-V and MT control conditions. Multilevel models are used to estimate autocorrelation across the three time points. We hypothesize that chronic grief will decrease more in the CGMI-V condition relative to the MT control condition. Caregiver sex, age, relationship to the care-receiver, as well as care recipient death or discharge from the facility, will be controlled for as covariates in the analysis. Sex and caregiver/care recipient relationship, as well as care recipient death or discharge from the facility, will be entered into the model as dummy-coded variables. We will examine the interaction effects (δ) to make certain that they are large

enough to justify a more robust clinical trial. While there is some likelihood of obtaining significant findings in this study, the primary purpose of this analysis is to estimate effect sizes.

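### The Aim 1–3 models state neither a baseline-score covariate nor a common baseline mean, so the treatment-effect interval may be wider than the data support

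*Combined protocol and SAP*

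**What the plan says.** Section 9.5, Aim 1, states: "Multilevel linear models will be run for the CGMI-V and MT control conditions". The models span the three assessments, baseline included, and the quantity to be examined is an interaction effect. On adjustment it says: "Caregiver sex, age, relationship to the care-receiver, as well as care recipient death or discharge from the facility, will be controlled for as covariates". Baseline MM-CGI score is not in that list, and nothing says whether the two arms share a baseline mean. Aims 2 and 3 are said to parallel Aim 1 with other outcomes.

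Later in 9.5, under Aim 4, the plan proposes residualized change scores, meaning observed score minus the score predicted from baseline, and says they will be used across its analyses.

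Section 9.2.1 says: "Randomization will be stratified in six Waves of 24 participants each", with exactly 12 per condition in each wave. Wave appears in no analysis model.

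Section 9.2 puts precision ahead of power as the design criterion, and 9.5 says the reported result will be an effect size with its confidence interval.

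**The concern.** In a randomised trial the arms have the same expected baseline mean. A model that nonetheless estimates a separate baseline mean for each arm, and takes the effect from condition by time, compares changes from baseline. That is valid, but it carries the full noise of the baseline measurement into the contrast. Entering baseline as a covariate, or constraining the arms to one baseline mean, is also unbiased under randomisation. Apart from a trivial degrees-of-freedom cost, it is at least as precise.

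Interval width is what this trial is designed around, so the choice bears directly on its main product, the primary effect size and its interval. It also affects all the secondary outcomes. What is at stake is efficiency and a uniquely specified model, not bias.

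A smaller matter is that allocation is stratified by wave while the analysis ignores wave.

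**Working it through.** **Inputs**
- SD: "The standard deviation associated with total grief as measured with the MM-CGI is around 35.78 raw units" (9.2).
- Analysable number: 64 per arm (9.2).
- Level: "A two-tailed 0.05 significance level will be used for all statistical tests" (9.5), so z = 1.96.
- Correlation r between baseline and follow-up: not given. Section 9.1 reports for the MM-CGI test-retest "scores range from .71 to .75, indicating stability of the measure over time in all three subscales". I use .71 to .75 as a proxy and show .50 and .80 as a wider range.
- Further assumptions: equal SD at baseline and follow-up; clustering within the video groups ignored at first.

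**Step 1: the plan's own figure.** Section 9.2 gives a standard error of about 4.47, "producing confidence intervals between -8.77 and +8.77 units". This reproduces as 35.78/√64 = 4.47 and 1.96 × 4.47 = 8.77. That is the half-width for the mean of one arm.

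**Step 2: the unadjusted two-arm difference.** 1.96 × 35.78 × √(2/64) = 12.40 units, and 12.40/35.78 = 0.35 SD.

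**Step 3: two ways of using baseline.** The formulas are for the contrast at a single follow-up visit.
- Baseline means free by arm (difference in changes): 12.40 × √(2(1 − r)).
- Baseline as covariate (a common baseline mean is about as precise): 12.40 × √(1 − r²).
- Ratio of adjusted to free: √((1 + r)/2), which does not depend on n or SD.

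| r | Free baseline | Adjusted | Ratio |
|---|---|---|---|
| .50 | 12.40 | 10.74 | 0.866 |
| .71 | 9.44 | 8.73 | 0.925 |
| .75 | 8.77 | 8.20 | 0.935 |
| .80 | 7.84 | 7.44 | 0.949 |

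At r = .71 to .75 the adjusted interval is 7.5% to 6.5% narrower. The variance ratio (1 + r)/2 is 0.855 to 0.875. The gain is therefore worth 1/0.855 = 1.17 to 1/0.875 = 1.14 times the sample, that is, 17% to 14% more participants.

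**Step 4: clustering.** Six waves with two groups each give 12 groups, or 64/12 = 5.33 analysed per group, in the CGMI-V arm only. At an assumed intraclass correlation of .05, both columns are multiplied by √((2 + 4.33 × .05)/2) = 1.053. For r = .71 to .75 the free-baseline half-width becomes 9.94 to 9.23 and the adjusted one 9.19 to 8.63. On this approximation the ratio is unchanged.

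**Step 5: wave and time since placement.** A simulation of 1,500 trials took r = .73, with wave explaining 3% and placement 5% of variance (both assumed). Adding the two as main effects changed the half-width as follows:
- free-baseline interaction: 9.01 to 9.01;
- common-baseline model: 8.55 to 8.52;
- baseline as covariate: 8.57 to 8.56.

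The change is 0.00 to 0.03 units.

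**The case against.** The strongest reply is that the plan never says baseline means are free by arm. A multilevel model over three time points with an interaction term is compatible with a common baseline mean, which would lose nothing. The residualized change scores under Aim 4 are themselves a form of baseline adjustment and are described as applying broadly. This stands in part, because the loss is conditional on the model form. It does not settle the matter. The residualized scores sit in the mediation text, and an outcome already residualized on baseline does not fit a model in which baseline is one of three repeated outcomes. The two parts of 9.5 need reconciling whichever was meant.

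A reader might infer that baseline adjustment is needed to reach the plan's ±8.77. The documents do not support that. The figure is a one-arm half-width, and its unadjusted two-arm counterpart is 12.40, so it is not a valid target for the treatment contrast. The free-baseline result of 8.77 at r = .75 matches only because 2(1 − .75) × 2/64 = 1/64.

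A reader might also infer that omitting wave and time since placement costs precision. Step 5 shows almost no gain from them as main effects. With 12 to 12 in every wave, leaving wave out keeps the arms balanced and makes the model standard error, if anything, slightly conservative. The plan records "time since placement in the LTCF" under Background Measures, and Aim 1 opens by saying background variables will be controlled for, so placement may already be intended. Nothing in the documents shows that either variable predicts change in grief. Crossing both with three visits would bring the added parameters to 18 (5 + 10 for wave, 1 + 2 for placement) without a demonstrated return.

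**Conclusion.** The point holds as a gap in specification with a modest, avoidable cost. As written, Aims 1–3 do not commit to any use of baseline beyond its role as a repeated outcome. If baseline means are left free by arm, the primary interval is wider than it need be: 9.44 to 8.77 units against 8.73 to 8.20 at r = .71 to .75. The direction holds at every correlation shown; the size depends on r.

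The .71 to .75 values are subscale test-retest figures with no stated interval. They are not total-score correlations over 8 or 24 weeks, and screening on grief could lower them. Absolute widths would also grow with group clustering. No bias in the planned estimate is shown. The case for wave is agreement between analysis and allocation only.

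**What to change.** In Aim 1, and by reference in Aims 2 and 3:

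- Specify a model with visit as a categorical factor and either one baseline mean common to both arms or baseline score of the outcome as a covariate.
- Report the treatment contrast and its confidence interval separately at 8 and at 24 weeks.
- State whether the residualized change scores apply to Aim 4 only, so that 9.5 describes one primary model.
- Add wave as a fixed main effect.

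All the data are already collected, so the cost is SAP wording. Wave takes five degrees of freedom (six waves minus one) from about 128 analysed participants. No visit interactions with wave or placement are requested.

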Control condition. Caregivers in the control condition will receive Minimal Treatment (MT) consisting of written information about late-stage ADRD (Alzheimer's Association) at baseline. The Project Director will mail caregivers in the MT control condition all written information materials.

4 **SELECTION AND ENROLLMENT OF PARTICIPANTS**

We will recruit a sample of 144 ADRD caregivers who have a family member residing in dementia care or memory care units in long-term care facilities located in the Chicago metropolitan area. We have well-established collaborating relationships with 35 long-term care facilities that will give us access to a diverse pool of approximately 1,000 ADRD family caregivers.

4.1 **Inclusion Criteria**

Participants must meet all inclusion criteria listed below in order to participate in this study.

- 21 years of age or older
- Identified as family member, fictive kin (self-identified family member) or partner of care recipient at any time post permanent placement of care in LTCF
- Care recipient has a documented ADRD diagnosis and resides in any type of unit in a long-term care facility
- Possessing self-reported basic computer literacy and in-home internet access
- Able to speak, read, and write English
- Not currently attending another ADRD caregiver grief management group

- Experiencing high to moderate levels of grief per screening with the Marwit-Meuser Caregiver Grief Inventory-Short Form (scores 25 or above), and/or experiencing high levels of depressive symptoms per screening with PHQ9 (scores 10 or above)
- Caregivers whose care recipients die during the course of the intervention will remain in the study

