Aim 2. Controlling for background variables, compare the effect sizes of the CGMI-V condition and MT control condition on changes in secondary caregiver mental health outcomes: depression symptoms and anxiety symptoms and positive states of mind. We hypothesize that one dependent measure (positive states of mind) will increase more and the other two (depression symptoms and anxiety symptoms) will decrease more in the CGMI-V group relative to the MT control condition.

Apart from the dependent measures examined, this analysis will parallel that described in Aim 1. As in Aim 1, the primary goal of this analysis is to estimate effect sizes associated with the CGMI-V.

Aim 3. Controlling for background variables, compare the effect sizes of the CGMI-V condition and MT control condition on secondary facility-related outcomes: caregiver satisfaction with care and conflict with staff in the LTCF. We hypothesize that caregiver satisfaction with care will increase and that conflict with staff in the LTCF will decrease in the CGMI-V condition relative to the MT control condition.

Apart from the dependent measures examined, this analysis will also parallel that described in Aim 1. As in Aim 1, the primary goal of this analysis is to estimate effect sizes associated with the CGMI-V.

Aim 4. Examine the mediating effects of chronic grief exacerbators on chronic grief, mental health, and facility-related outcomes. We hypothesize that improvement in chronic grief exacerbators will mediate the improvements in caregiver chronic grief, mental health, and facility-related outcomes.

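### The primary model adjusts for care-recipient death or discharge, which follow randomisation; if assignment affects discharge, some codings no longer give the total effect of assignment

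*Combined protocol and SAP*

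**What the plan says.** In section 9.5, Aim 1 is framed as an effect on change in chronic grief with background variables controlled. The covariates are caregiver sex, age and relationship to the care recipient, "as well as care recipient death or discharge from the facility, will be controlled for as covariates in the analysis". The categorical terms, including death or discharge, "will be entered into the model as dummy-coded variables"; nothing more is said about coding. Aim 2 follows the same model ("this analysis will parallel that described in Aim 1"), and so does Aim 3 ("this analysis will also parallel that described in Aim 1"). The same section states: "All analyses will be performed on an intent-to-treat basis".

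Elsewhere, section 9.1 treats background information as something measured at entry: "To describe caregiver and care recipient baseline background data, we will collect standardized information". The inclusion criteria (section 4.1) require a care recipient who "resides in any type of unit in a long-term care facility", and add: "Caregivers whose care recipients die during the course of the intervention will remain in the study". The change-in-status survey is scheduled at 8 and 24 weeks only (sections 6.1, 6.2.2 and 6.2.3).

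**The concern.** A care recipient who is a facility resident at entry can die or be discharged only later, and change of status is first recorded at week 8. The covariate is therefore a post-randomisation event placed in a list of background variables. Adjusting for such an event can remove part of the effect of assignment, or add to it, if assignment changes how often the event occurs.

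The plan itself suggests a route for discharge. Hypotheses 3.1 and 3.2 expect CGMI-V to raise satisfaction with care and reduce conflict with staff, and either could bear on whether a family moves the care recipient. No comparable route is apparent for death.

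The trial's declared product is an effect size used to judge whether a larger trial is justified. With the coding open, two analysts could follow the text and report different effect sizes from the same data, and the plan gives no analysis without the covariate.

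**Working it through.** **The plan's own precision figure (section 9.2).** SD 35.78, 64 per condition: 35.78/√64 = 4.47; × 1.96 = 8.77 points; 8.77/35.78 = 0.245 SD, the stated .25. It reproduces, and serves as the yardstick here. (It is the standard error of one arm's mean. For a difference between two arms of 64, 35.78 × √(2/64) = 6.33 and the half-width is 12.40 points, or 0.35 SD, before any gain from repeated measures. That is a separate matter.)

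**Formula.** In a linear model without interactions, and with no unmeasured common cause of the event and grief, adjusted minus total effect = −γ(p₁ − p₀). Here γ is the effect of the event on grief and p₁, p₀ are the event rates in CGMI-V and control. If the rates are equal, the difference is zero.

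**Assumed inputs.** The documents give no event rates and no event effect, so every input in this and the remaining checks is an assumption:
- 12% vs 9%, γ = 0.5 SD: 0.5 × 0.03 = 0.015 SD; × 35.78 = 0.5 points.
- 12% vs 6% (about 9 vs 4 of 72), γ = 0.8 SD: 0.8 × 0.06 = 0.048 SD; 1.7 points.
- 15% vs 5%, γ = 0.8 SD: 0.8 × 0.10 = 0.08 SD; 2.9 points.

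**Does coding matter?** Simulation of a random-intercept model: three visits, complete data, within-person correlation 0.6, effect of −0.40 SD apart from the event, one third of events by week 8. Week-24 arm-by-time effect in SD:

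| Event rate, control vs CGMI-V; γ | Unadjusted | Person-level dummy | Time-varying dummy |
|---|---|---|---|
| 12% vs 12%; 0.8 | −0.400 | −0.400 | −0.400 |
| 12% vs 9%; 0.5 | −0.418 | −0.418 | −0.403 |
| 12% vs 6%; 0.8 | −0.449 | −0.449 | −0.401 |
| 6% vs 12%; 0.8 | −0.357 | −0.357 | −0.404 |
| 15% vs 5%; 0.8 | −0.479 | −0.479 | −0.399 |

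The unadjusted column is the total effect. A fixed person-level main effect cancels from within-person change, so it does not move the arm-by-time effect. A time-varying dummy does, in either direction.

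**Baseline-adjusted follow-up model.** Here a person-level dummy shifts the estimate too: −0.449 to −0.402 at 12% vs 6%, and −0.479 to −0.398 at 15% vs 5%. This is relevant because the Aim 4 text of section 9.5 proposes residualised change scores for all of the analyses.

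**Harsher assumptions.** In a single-follow-up regression with γ up to 1.0 SD and an unmeasured common cause of event and grief, the gap reached 0.139 SD (5.0 points) at 15% vs 5%. It was still zero at equal rates.

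**One dummy or two.** With deaths at 10% in both arms (+0.8 SD) and discharge at 12% vs 6% (−0.4 SD), the estimate is −0.378 unadjusted, −0.363 with one combined dummy, and −0.402 with separate dummies. The combined dummy gives neither the total nor the adjusted effect.

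**Price of leaving death out.** With equal deaths of 10%–20%, 0.5–0.8 SD per death, 64 per arm and within-person correlation 0.5–0.7, the standard error is 1.006 to 1.081 times as large, that is, about 1%–8% larger. Chance imbalance in deaths has an SD of √(2 × 0.10 × 0.90/64) = 0.053 to √(2 × 0.20 × 0.80/64) = 0.071. Multiplied by 0.5 and 0.8 SD respectively, that is 0.027 to 0.057 SD.

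**The case against.** The plainest reading of Aim 1 may produce no shift at all. Death or discharge stands beside sex and relationship as a dummy in a three-visit model judged on its interaction effects, and missing data are imputed. If the dummy is a fixed person-level main effect, the arm-by-time effect does not move. The residualised scores appear in the mediation text, while Aim 1 names a different model. This stands as a reason to expect little consequence, but the text does not fix the coding.

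The link between arm and discharge is conjecture. Placement must be permanent at entry, and the assumed discharge rates have no source. This also stands.

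Removing the covariate is not free. In the central scenario at 64 per arm, root mean squared error for the total effect was 0.167 unadjusted and 0.165 with time-varying adjustment. Dropping discharge while keeping a time-varying death indicator showed no bias, at 0.161 to 0.164. Section 2.2 gives a prognostic reason to keep death: in an earlier grief intervention, gains were not sustained where the spouse had been placed or had died. The objection therefore succeeds against treating death and discharge alike.

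A reader might infer that the plan breaches its intent-to-treat statement. The documents do not support that. Caregivers stay in after a care recipient's death, and those who drop out or withdraw are asked to continue assessments (sections 4.1, 6.2.3 and 8). The analysis set is intact. What is open is which effect is estimated, and reading the statement as a commitment to the total effect is itself an inference.

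**Conclusion.** The point holds in a limited form. Death and discharge are post-randomisation events and do not belong among background variables. For discharge the case for moving the adjustment is clear; for death it is weak, since an arm effect is implausible and the event is likely to be prognostic.

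A reader might go further and conclude that the primary estimate will be biased. The documents do not show this: bias requires both an arm effect on the event and a coding that lets it through, and neither is established. Under the main assumed rates the shift is 0 to about 0.08 SD (0 to 2.9 points), small beside the stated .25 SD; harsher assumptions give up to 0.14 SD. All the simulations concern a standardised grief score. Nothing was computed for the Aim 2 and 3 outcomes.

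Aim 3 raises a further question. Its outcomes rate care in the facility and conflict with its staff, which are no longer current once the care recipient has died or left.

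This is a point to consider, not a fault that undermines the trial.

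**What to change.** - **Aims 1 and 2:** take discharge out of the primary model and use the baseline covariates already named (sex, age, relationship).
- **Sensitivity analysis:** pre-specify the model with separate death and discharge indicators, each defined from status at each visit, and report event counts by arm.
- **Death:** by default it moves to the sensitivity analysis. Keeping a time-varying death indicator in the primary model is acceptable and recovers the precision lost without it. State the choice before analysis.
- **Aim 3:** do not simply carry the Aim 1 wording across. Also state how satisfaction and conflict scores recorded after death or discharge are treated.

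The cost is SAP wording only, with no added visits or sample size. The status survey is already scheduled at 8 and 24 weeks. Its form is not in the documents, so confirm that it records death and discharge separately. If death also leaves the primary model, accept the standard error increase of about 1%–8% (assumed inputs) and some unadjusted chance imbalance in deaths, which the sensitivity analysis would show.

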The focus of the proposed study is on change in chronic grief, mental health, and facility-related outcomes between measurement points and change in chronic grief exacerbators as a mediating variable. Thus, we propose to use residualized change scores (i.e., the difference between the observed score of a variable and the predicted score based on the baseline measure of that variable) throughout the analyses. These scores have the advantage of evaluating change between measurement points without concerns about regression toward the mean that are associated with standard change scores and have the advantage of reducing the number of variables in the model. In general, the analytic model will include covariates to control for background characteristics of the participants and time since baseline. The mediation effects of changes in chronic grief exacerbators (lack of knowledge, sense of loss, guilt, and role captivity) on three outcome measures (chronic grief, mental health, and facility-related outcomes) will be examined in three separate models. The regression mediation models described in MacKinnon⁷⁶ will be used to estimate these effects. The null hypothesis is that changes in chronic grief exacerbators will not mediate any of the three outcome

measures. As mentioned in the first three aims, the primary goal of this analysis is to estimate the size of these mediation effects, rather than to obtain statistically significant differences.

In accordance with NIH policy we will perform an analysis to estimate effect sizes associated with CGMI-V intervention between gender and racial/ethnic subgroups.

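### Aim 4 scores each variable as a residual from its own baseline and, read naturally, leaves the baseline scores out of the mediation models, which can bias the mediated effect, usually toward zero

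*Combined protocol and SAP*

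**What the plan says.** Section 9.5, Aim 4, proposes residualized change scores for outcomes and mediators alike, defined as the gap between the observed score and the "predicted score based on the baseline measure of that variable) throughout the analyses". Each variable is therefore residualised on its own baseline only. Two reasons are given: avoiding the regression to the mean that affects raw change scores, and that these scores "have the advantage of reducing the number of variables in the model".

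On adjustment, the section says that "the analytic model will include covariates to control for background characteristics of the participants and time since baseline". Section 9.1 describes background measures as socio-demographic and situational items ("To describe caregiver and care recipient baseline background data, we will collect standardized information"), not baseline scores on the grief, mental health or exacerbator scales.

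The mediator is framed as "change in chronic grief exacerbators as a mediating variable". The aim is one of estimation: "the primary goal of this analysis is to estimate the size of these mediation effects", rather than a significance test.

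**The concern.** Residualising follow-up grief on baseline grief, and follow-up guilt on baseline guilt, removes from each variable only what its own baseline predicts. The mediator residual can still carry baseline outcome. If a caregiver's baseline grief helps to predict later guilt beyond baseline guilt, that part stays in the mediator residual although it has been removed from the outcome residual. The mediator-to-outcome slope is then distorted. A regression with both baselines in both equations does not have this problem.

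The deliverable of Aim 4 is the size of the mediated effect, so a bias in size is a bias in the result itself. Whatever is lost from the mediated path is reported as a direct effect of the intervention, which would suggest that the exacerbators explain less of it than they do.

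**Working it through.** **Inputs from the documents.** Section 9.2 gives 64 evaluable per condition and 10% attrition. 64 / 0.9 = 71.1, rounded up to 72, which reproduces the plan's enrolment figure and leaves 2 × 64 = 128 evaluable. The plan states no figure for Aim 4. It gives no baseline correlation, mediator stability, cross-effect or slope, so everything below is assumed and shown over a range.

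**Model.** X is arm, M the mediator and Y the outcome. Baselines M0 and Y0 have unit variance and correlation ρ.

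- M1 = aX + s·M0 + g·Y0 + e
- Y1 = c′X + b·M1 + h·Y0 + d·M0 + u

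Here s is mediator stability, g is the cross-effect of baseline outcome on the later mediator given baseline mediator, b is the true slope, and d is any direct effect of baseline mediator on later outcome. Setting Ve = Var(e) = 1 − (s² + g² + 2sgρ) keeps the within-arm mediator variance at 1.

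**Own-baseline residuals.** Arm is randomised, hence independent of both baselines.

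- rM = aX + g(Y0 − ρM0) + e
- rY = (c′ + ab)X + (bs + d)(M0 − ρY0) + b·e + u

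The covariance of (Y0 − ρM0) with (M0 − ρY0) is −ρ(1 − ρ²). Regressing rY on X and rM therefore gives

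b_res = [b·Ve − g(bs + d)ρ(1 − ρ²)] / [Ve + g²(1 − ρ²)].

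**One case in full** (b = 0.30, s = 0.6, ρ = 0.5, g = 0.2, d = 0):

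- Ve = 1 − (0.36 + 0.04 + 0.12) = 0.48
- numerator = 0.144 − 0.2 × 0.18 × 0.375 = 0.1305
- denominator = 0.48 + 0.04 × 0.75 = 0.51
- b_res = 0.256, and 0.256 / 0.30 = 0.85, so 15% too small.

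**Ratio b_res / b, with b = 0.30 and s = 0.6:**

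| g | d | ρ = 0.3 | ρ = 0.5 | ρ = 0.7 |
|---|---|---|---|---|
| 0 | 0 | 1.00 | 1.00 | 1.00 |
| 0.1 | 0 | 0.96 | 0.95 | 0.95 |
| 0.2 | 0 | 0.88 | 0.85 | 0.86 |
| 0.3 | 0 | 0.75 | 0.69 | 0.68 |
| 0.1 | −0.3 | 1.00 | 1.01 | 1.02 |
| 0.2 | −0.3 | 0.97 | 1.00 | 1.02 |
| 0.3 | −0.3 | 0.91 | 0.95 | 0.99 |
| −0.2 | 0 | 0.99 | 1.02 | 1.03 |
| −0.2 | −0.3 | 0.92 | 0.92 | 0.94 |

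The rows with d = −0.3 = −b are those in which the outcome responds to change in the mediator.

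**Where the loss goes.** The arm-to-mediator path and the total arm effect are unaffected, so the reported direct effect is c′ + a(b − b_res). With a = 0.4 and c′ = 0, the true indirect effect is 0.4 × 0.30 = 0.12. At g = 0.3, ρ = 0.5 and d = 0, the spurious direct effect is 0.4 × (0.300 − 0.207) = 0.037.

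**Second set of assumptions** (a = 0.5, b = 0.4, true indirect effect 0.200, s = 0.5), simulated at n = 128 with 3,000 runs per scenario. At ρ = 0.5 and d = 0, the residual-score method averaged 0.196, 0.189, 0.177 and 0.155 for g = 0, 0.1, 0.2 and 0.3. Regression with both baselines in both equations averaged 0.198 to 0.201 in all nine scenarios run. Over the full closed-form grid for this set, the residual-score slope was at worst 31% too small and at most about 6% too large.

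**Precision at n = 128** (first set, ρ = 0.5, d = 0, true indirect effect 0.12). Root mean squared error, residual-score against both-baselines: 0.050 / 0.051 at g = 0, 0.050 / 0.051 at 0.1, 0.048 / 0.049 at 0.2 and 0.057 / 0.049 at 0.3.

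**The case against.** Four objections have force.

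- **The omission is inferred.** The covariate sentence opens as a general statement, the section defers to a cited text on mediation regression, and nothing expressly excludes the baseline scores. That stands. Still, keeping them would cancel the saving in variables that the plan gives as a reason for using these scores.
- **The direction is not guaranteed.** A reader might infer that Aim 4 necessarily understates mediation. The documents do not support that. If baseline outcome is related to the later mediator only through baseline mediator, there is no bias. If the outcome responds to mediator change, which is close to the plan's own framing, the bias is small and can reverse slightly.
- **Sampling error is large.** At n = 128 the sampling SD of the indirect effect is about 0.05, roughly 40% of an effect of 0.12. Up to a cross-effect of 0.2 the planned method has no larger root mean squared error than the alternative. This limits the practical gain but does not favour the planned method. Its bias would not shrink with more participants, and the adjusted model costs almost nothing in precision.
- **Aim 4 is exploratory** (Sections 1.2 and 3), and avoiding regression to the mean is a fair motive. Both are true, but baseline adjustment meets that motive equally well.

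A reader might also cite the modest reliabilities in Section 9.1 against residual scores. Unreliable mediators attenuate the both-baselines model almost equally, so they are a separate matter and do not help to choose between the methods.

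**Conclusion.** The concern holds in conditional form. Own-baseline residuals without the baseline scores in the model are not equivalent to adjusting for both baselines. The mediated effect is biased, usually toward zero, when baseline outcome predicts the later mediator over and above baseline mediator. With slope 0.30, stability 0.6, baseline correlation 0.3 to 0.7 and no direct baseline-mediator effect, the shortfall is about 4-5%, 12-15% and 25-32% at cross-effects of 0.1, 0.2 and 0.3. It is nil at zero cross-effect.

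The mechanism follows from the algebra. The size is uncertain because every input to it is assumed, and the omission of the baselines is the natural reading rather than a stated rule. The point is confined to Aim 4 and to the mediator-to-outcome path. The change is worth making because, in these models, adjustment for both baselines is right whatever the cross-effect, while the planned scores are right only in special cases.

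**What to change.** In Section 9.5, Aim 4, replace the residualized change scores with follow-up scores and specify both equations:

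- **Mediator equation:** follow-up mediator on arm, baseline mediator(s), baseline outcome and the listed covariates.
- **Outcome equation:** follow-up outcome on arm, follow-up mediator(s), baseline mediator(s), baseline outcome and the listed covariates.

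Estimate the indirect effect from these two equations. If the investigators prefer to keep residual scores, adding both baselines to both equations gave the same estimates in the simulations. In either case, state explicitly that the baseline scores are in the model.

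The cost is a wording change and two extra terms per equation with a single mediator, or five if all four exacerbators enter together (four baseline mediators plus baseline outcome), with about 128 evaluable participants. No new data are needed: Section 6.1 already schedules every one of these scales at baseline, 8 weeks and 24 weeks.
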